3.3 Randomization

Study staff use pre-generated randomization tables for 1:1 allocation of participants to each study arm using a permuted block design with a block size of four. Pre-generated randomization tables are created using standard statistical software (e.g. computerized random block and sequence generation) by the MVP-ROAR-FH Study data manager, under the direction of the

biostatistician, and stored in a secure file share accessible to select study staff. Randomization occurs upon the completion of baseline procedures and confirmed receipt of each participant's DNA specimen and is mechanized through a computerized randomization tool. Study staff enrolling and allocating participants to study treatments are blinded to the pre-generated randomization tables.

3.4 Data sources, collection, and storage

Study outcomes data will be collected from the VA Corporate Data Warehouse (CDW), a repository of administrative and clinical data from the VA's nationally deployed electronic health record (EHR) system;³ clinical chart review of the EHR, participant baseline and follow-up surveys, clinical confirmation genetic testing, and trial operations data recorded by the study team. All study data will be stored, cleaned, and analyzed within a secure VA computing environment and will be accessible to authorized study staff only.

3.5 Stopping guidance

This study has no stopping rules. Enrolled participants may withdraw from the study at any time.

3.6 Protocol deviations

Protocol deviations are characterized as circumstances that depart from planned study procedures and anticipated events (e.g., participant withdrawal, loss to follow-up). Protocol deviations may include, but are not limited to, the following:

1. Deviation from inclusion or exclusion criteria (e.g., ineligible patient enrolled and/or randomized)
2. Patient receipt of treatment other than treatment as randomized

The number of ineligible patients randomized, patients receiving a treatment other than as randomized, or other yet to be determined protocol deviations, if any, will be characterized and reported in the final manuscript(s). For the purposes of primary and secondary outcomes, data from patients who experience a protocol deviation will be included in the final data sets. Their outcomes data will be analyzed as part of the treatment group to which they were randomly allocated. The inclusion or exclusion of these patients' data in subsequent secondary or subgroup analyses will be detailed in the final manuscript(s) as needed.

3.7 Adverse events

Adverse events (AEs) related to MVP-ROAR-FH procedures do not include anticipated events related to blood draws (e.g., pain, minor bleeding, bruising, fainting, or lightheadedness) and minor feelings of discomfort while answering survey questions. Pre-existing conditions or illnesses which are expected to exacerbate or worsen are also not considered adverse events and will be accounted for in the subject's medical history. An AE may be considered any other unanticipated or unintended medical occurrence or worsening of a sign or symptom (including an abnormal laboratory finding other than the return of genetic information associated with FH) or disease in a study subject, which does not necessarily have a causal relationship with the study condition, procedure(s) or study agent(s), that occurs after participant informed consent is obtained. A serious adverse event (SAE) will be defined as an AE resulting in one of the following outcomes: death during the 6 months after study enrollment, life threatening event

(defined as an event that places a participant at immediate risk of death), inpatient hospitalization, and any other condition which, in the judgment of the PI, represents a significant hazard, such as an important medical event that does not result in one of the above outcomes. An event may be considered an SAE when it jeopardizes the participant or requires medical or surgical intervention to prevent one of the outcomes listed above. AEs may be observed by the study staff or volunteered by participants, their family members, their PCPs, or others. All AEs and SAEs will be assessed for relationship to the study research procedures by the study PI, to determine whether study participation was likely to have caused the AE/SAE.

4.0 Trial Population

The overall study population includes all participants of the Million Veteran Program (MVP) mega-biobank research study.

4.1 Study inclusion and exclusion criteria

Inclusion criteria: A participant is eligible for enrollment in this study if he/she meets the following criteria:

- Is a living enrollee in MVP.
- Is identified to have a pathogenic or likely pathogenic variant in an FH-associated gene in their MVP genotype data.
- Has not previously undergone genetic testing for familial hypercholesterolemia. Study staff first ascertain this by review of the medical record and then confirm during the informed consent call by asking the participants about any prior genetic testing he/she has undergone.
- Is not incarcerated.
- Is not pregnant.

4.2 Screening, recruitment, and withdraw

MVP Core study staff queries MVP databases for living participants with an eligible FH variant. The MVP Core study team mails eligible participants a letter introducing this new MVP-related study giving participants the opportunity to opt out of further contact by returning a prepaid opt out postcard or by calling the MVP Call Center. To any participant who does not opt out within 2 weeks of this initial mailing, the MVP-ROAR-FH study team mails a letter providing more detail about the study, including all necessary informed consent information. Two weeks after this mailing, the study genetic counselor calls the participant to review the informed consent information, answers any questions about the study, and documents verbal consent or decline. See MVP-ROAR-FH Study protocol VA CIRB 19-11 for additional detail regarding the study recruitment process.

Duration of the study recruitment period, the total number of patients screened, the number of screened patients not recruited and reason for non-recruitment, and other screening and recruitment metrics will be collected and reported for the overall study. In addition to protocol deviations and AEs or SAEs, if any, the number, and reasons (if known) for participant withdrawal and/or loss to follow-up prior to the conclusion of the study's period of enrollment will be reported in the final manuscript(s). Participant flow will be reported in the final manuscript

using CONSORT guidelines for the reporting of clinical trials.^{4,5}

4.3 Reference start and end dates

Participant study enrollment occurs on the date of consent. Randomization occurs upon completion of baseline procedures (i.e. baseline survey) and confirmed receipt of DNA biospecimen (blood or saliva). Study participation concludes upon completion of the 6-month biospecimen collection and end-of-study survey, conducted approximately 6 months after the date of randomization and end-of-study survey.

4.3.1 Baseline assessment

For the purposes of outcomes assessment, baseline is defined as the most recent measurement of a study-related outcome (see Section 6.0) on or prior to a participant's date of randomization, unless otherwise specified. The total number of participants with baseline measurements obtained post-randomization and/or any statistical analysis including a baseline measurement obtained post-randomization will be reported.

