4.5 Baseline patient characteristics

Baseline characteristics will be summarized and presented for participants in the ITT populations. Standard statistical summaries, depending on data type and distribution, will be presented as 1) total numbers of participants with each characteristic (n) and as a proportion (%) of each group stratified by randomization arm or 2) as means and standard deviations (if normally distributed) or medians and interquartile ranges (IQR) (if non normally distributed) stratified by randomization arm. No statistical testing will be carried out for participant baseline characteristics or measures between treatment groups.

At minimum, the below participant baseline characteristics, including the pre-specified baseline measurements of the study outcomes described in Section 6.0, will be derived and reported:

| Baseline characteristic | How derived | Presentation |
|---|---|----------------------------------|
| Age in years | As calculated using EHR administrative data relative to date of consent and enrollment. | mean (SD) / median (IQR) |
| Gender / Sex | As determined by EHR administrative data. | n (%) |
| Race | As determined by EHR administrative data and/or data collected from baseline survey. | n (%) |
| Ethnicity | As determined by EHR administrative data and/or data collected from baseline survey. | n (%) |
| Socioeconomic Status / Area Deprivation Index | Calculated using income, geographic, and other EHR administrative data.(ADI) ⁹ | n (%) |
| Self-reported health status and quality of life | As determined by data collected from baseline survey. (VR-12) ¹⁰⁻¹² | mean (SD) / median (IQR) |
| Self-reported patient activation | As determined by data collected from baseline survey. (PAM-13) ¹³ | mean (SD) / median (IQR) / n (%) |
| Beliefs about medications | As determined by data collected from baseline survey. (Beliefs About Medicines Questionnaire) ¹⁴ | mean (SD) / median (IQR) |
| Low-density lipoprotein cholesterol | As determined by EHR data. | mean (SD) / median (IQR) |
| Lipid-lowering pharmacotherapy | As determined by data collected from baseline survey and EHR data. | n (%) |

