6.0 Outcome definitions and timing

6.1 Primary outcome (6-month difference in LDL-C)

Baseline (at enrollment) and end-of-study (at 6 months) LDL-C values are defined as the LDL-C measurements obtained from study-related blood draws as processed by the study's centralized laboratory. For participants for whom it is not feasible to visit their local VA facility for a blood draw at baseline, a documented LDL-C value in their medical record may be used for a study measurement, provided it is not older than 6 months from their date of enrollment and a change in lipid-lowering therapy has not occurred between the clinical LDL-C value and study enrollment. For participants for whom it is not feasible to visit their local VA facility for an end-of-study blood draw, a documented LDL-C value in their medical record may be used for a study measurement. The documented LDL-C value closest to the date 6 months after the date of randomization will be used for the end-of-study value. If no 6-month value is available, the study may use an LDL-C value obtained from the medical record during the 6-month observation period, including carry forward of the baseline value.

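### Baseline LDL-C is tied to two different dates with no rule for a late draw, so an Immediate-arm baseline taken after disclosure of results could enter the primary change score

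*SAP*

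**What the plan says.** **General rule.** SAP Section 4.3.1 sets a default that gives way wherever another rule is stated: "baseline is defined as the most recent measurement of a study-related outcome (see Section 6.0) on or prior to a participant's date of randomization". The same section says that the number of participants with later baselines will be reported, and that "any statistical analysis including a baseline measurement obtained post-randomization will be reported".

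**LDL-C rule.** SAP Section 6.1: "Baseline (at enrollment) and end-of-study (at 6 months) LDL-C values are defined as the LDL-C measurements obtained from study-related blood draws". If a baseline draw is not feasible, a medical-record value may be used "provided it is not older than 6 months from their date of enrollment" and if "a change in lipid-lowering therapy has not occurred between the clinical LDL-C value and study enrollment".

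**Dates.** SAP Section 4.3: "Participant study enrollment occurs on the date of consent", and "Randomization occurs upon completion of baseline procedures (i.e. baseline survey) and confirmed receipt of DNA biospecimen (blood or saliva"). Section 4.3.2 starts the 6-month clock at randomization.

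**Intervention and analysis.** Section 3.1 returns results at baseline in the Immediate Results arm and after 6 months in the Delayed Results arm. Section 7.2 compares mean change by an independent t-test, and Section 7.1 prespecifies no covariate adjustment.

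**Descriptive table.** Section 4.5 gives the source of baseline LDL-C as "As determined by EHR data".

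**The concern.** Two matters need to be kept apart.

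*Late study draws.* The SAP expects that some baselines may fall after randomization and asks only that they be reported. It does not say whether such an LDL-C value may enter the primary analysis, how late it may be, or whether it must precede disclosure of results. During the 6 months only the Immediate arm receives results, so only there can a late baseline already contain part of the response being measured. That part is then missing from the change score, and the between-arm difference shrinks.

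*Medical-record values.* Both eligibility checks end at consent, while follow-up is timed from randomization. If therapy changes in between, the record value passes both checks but no longer describes the participant at randomization. The resulting change score includes a response that has nothing to do with allocation.

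At stake are the size of the primary estimate (first matter), and its precision together with the per-arm mean changes promised in Section 5.1 (second matter).

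**Working it through.** **1. Can a baseline LDL-C fall after randomization under the text?**
- Section 4.2 has consent taken verbally by telephone, so a blood draw at a VA facility would ordinarily come after enrollment. The enrollment label in 6.1 therefore does not fix a latest date for the draw.
- Section 4.3 glosses baseline procedures as the survey and accepts saliva as the DNA specimen. A participant can meet both conditions without a lipid draw.
- Section 4.3.1 would exclude a later value by default, but it yields to other specifications and itself foresees later baselines. Section 6.1 states no cut-off at randomization.

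So the text leaves the possibility open. It does not say how often it happens.

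**2. The plan's own figure.** Inputs from Section 3.2: difference 20 points of percent change, SD 30, 80% power; two-sided alpha 0.05 from Section 5.1.

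n per arm = 2 × (1.960 + 0.842)² × (30/20)² ≈ 35.3, rounded up to 36, total 72. This matches the SAP. Power at 36 per arm is 80.7% (normal approximation).

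**3. Baselines drawn after disclosure.** Let f be the share of Immediate-arm baselines affected and s the part of the effect already realised at the draw. Both are assumptions.

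Measured difference = 20 × (1 − f × s)

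| f | s | Measured difference | Power, 36 per arm |
|---|---|---|---|
| 0 | – | 20.0 | 80.7% |
| 5% | 1 | 19.0 | 76.6% |
| 10% | 0.5 | 19.0 | 76.6% |
| 10% | 1 | 18.0 | 72.1% |
| 20% | 0.5 | 18.0 | 72.1% |
| 20% | 1 | 16.0 | 61.9% |

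The planned enrollment is larger: 244 in total, or 97 per arm after 20% loss. With 97 per arm:
- true difference 20: power is 99.6% with no late values and still 96.0% at f = 20%, s = 1;
- true difference 10 (the 50% non-escalation allowed for in Section 3.2 halves the effect): power is 64.1% with no late values, 55.1% at f = 10%, s = 1, and 45.9% at f = 20%, s = 1.

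The proportional loss f × s does not shrink with sample size. In numbers of people, 5% of 122 Immediate-arm participants is about 6 and 10% is about 12.

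**4. Therapy change between consent and randomization.** Let g be the share, equal in both arms, whose record baseline precedes a therapy change that lowers LDL-C by D points. Again both are assumptions.

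Shift in each arm's mean change = −g × D; SD = √(30² + g(1 − g)D²)

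- g = 10%, D = 20: shift −2 points, SD = √(900 + 36) = 30.6, power at 36 per arm 79.2%.
- g = 10%, D = 40: shift −4 points, SD = √(900 + 144) = 32.3, power at 36 per arm 74.7%.

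The shift is the same in both arms, so the expected between-arm difference is unchanged.

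**The case against.** The defence has several good points.

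- **The default is sound.** Section 4.3.1 places baseline on or before randomization, treats a later value as an exception and requires it to be disclosed. It covers all Section 6 outcomes, surveys included, and does not name LDL-C. A reader might infer that the SAP adopts post-randomization LDL-C as an accepted baseline for the primary test. The text does not go that far; it lacks a rule for the exception.
- **Late does not mean contaminated.** Bias needs disclosure, then a therapy change, then time for LDL-C to respond. Section 3.1 includes confirmation testing in the intervention, so disclosure need not coincide with randomization. The inference that every post-randomization baseline biases the comparison is not supported.
- **The direction is conservative.** The loss is toward the null and would not by itself produce a false positive. At 97 per arm it hardly affects power for a 20-point effect.
- **The consent gap precedes allocation.** It concerns only participants using the record fallback and should affect both arms alike. It is not a source of between-arm bias.
- **Excluding every late value has a price.** A measured value taken before disclosure may be better than an imputed one, particularly as Section 5.5 still permits mean or median imputation.

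All of this limits the point. It does not supply the missing rule. Sections 4.3.1 and 6.1 use different anchor dates, reporting a contaminated baseline does not remove it from the t-test, and the SAP does not separate draws before disclosure from draws after it.

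**Conclusion.** The point stands in limited form. The SAP anchors baseline LDL-C to randomization in one place and to consent in another, requires no lipid draw before randomization, and gives no handling rule for a late value. An Immediate-arm value drawn after disclosure and a therapy response would bias the primary difference toward zero by the fraction f × s: 1-2 points out of 20 if 5-10% of baselines carry the full effect. Those shares are illustrative, and full effect is the worst case; the SAP gives neither the number of late baselines nor the time from randomization to disclosure.

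The consent-based record checks are a lesser defect: extra variance and a shift in the per-arm mean changes, with no expected bias between arms. The length of the consent-to-randomization gap is also not given.

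The source label in Section 4.5 might be read as a third baseline definition. It is only a label in a descriptive table, and the SAP does not say whether study laboratory results also reach the EHR, so it is a minor alignment point. No stated sample size is in error here.

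**What to change.** 1. In Section 6.1, define baseline LDL-C as the last eligible value on or before randomization, consistent with Section 4.3.1.
2. Run both record-value checks (not older than 6 months, no change in lipid-lowering therapy) to the randomization date instead of the enrollment date.
3. In the primary analysis, do not use as baseline any LDL-C drawn after results were disclosed. Use the latest eligible earlier record value; if there is none, treat baseline as missing and use multiple imputation, named in advance in place of the open choice in Section 5.5.
4. For values drawn after randomization but before disclosure, prespecify a sensitivity analysis and report the number by arm.
5. Align the LDL-C source in the Section 4.5 table with Section 6.1.

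The cost is SAP wording and the use of randomization and disclosure dates in deriving the variable. A few participants may end up with an older or imputed baseline. No sample size figure changes.

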4.3.2 End-of-study follow-up and period of observation

Enrolled participants will be observed for a total of 6 months. For the primary (change in LDL-C) and secondary (proportion meeting LDL-C targets) outcomes related to LDL-C, the end-of-study date will correspond to the date 6 months from the date of randomization. The most recent LDL-C value on or after this date, either associated with a completed study-related blood draw or LDL-C value extracted from CDW data (if unable to obtain an end-of-study specimen), will be used as the 6-month LDL-C value.

Similarly, for the secondary outcome associated with intensification of pharmacotherapy, the end-of-study date will correspond to the date 6 months from the date of randomization. All lipid-lowering related prescriptions, either derived from participant survey responses or extracted from CDW data, which are identified as active prior to or after the date of randomization and considered active either on or before the date 6 months from the date of randomization will be considered for analysis. Prescriptions are defined as active if they fall within a time window of one and a half times the total days supply (equivalent to a medication possession ratio of 0.67) from the prescription start date.⁶⁻⁸

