6.2 Secondary outcomes

6.2.1. Proportion meeting LDL-C targets

The proportion of participants meeting individualized clinically significant LDL-C targets (<100mg/dL for primary prevention and <70 mg/dL for secondary prevention) will be determined at 6 months, using the LDL-C values as described for the primary outcome in Section 6.1.

Secondary prevention will be defined as any patient with any of the following:

Pre-existing atherosclerotic disease (ASCVD): acute coronary syndrome in the prior 12 months, history of myocardial infarction, history of ischemic stroke, symptomatic peripheral artery disease including aneurysm, all of atherosclerotic origin.

Presence of any ASCVD risk factors: age ≥ 65 years; prior percutaneous coronary intervention; prior coronary artery bypass graft; other evidence of coronary artery disease; diabetes mellitus; hypertension; chronic kidney disease; current smoking; congestive heart failure; family history of premature ASCVD; elevated coronary artery calcium score, Lp(a), or apoB; or ankle-brachial index < 0.9 .

All other participants will be considered eligible for primary prevention.

The primary or secondary prevention status of each participant will be determined by clinician review of participant medical records through the end-of-study date. The clinician reviewer(s) will be blinded to randomization status. For each participant deemed eligible for secondary prevention, the clinician will record the reason(s) for eligibility in a study database.

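### For participants without an end-of-study draw, SAP 4.3.2 and 6.1 select the 6-month LDL-C by different rules with no precedence, and 4.3.2 can admit Delayed-arm values drawn after disclosure

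*SAP*

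**What the plan says.** Section 4.3.2 opens with "Enrolled participants will be observed for a total of 6 months" and sets the end-of-study date at 6 months from randomization. Its rule applies to two outcomes: "For the primary (change in LDL-C) and secondary (proportion meeting LDL-C targets) outcomes related to LDL-C". The value used is "The most recent LDL-C value on or after this date, either associated with a completed study-related blood draw" or, for those without a specimen, "LDL-C value extracted from CDW data (if unable to obtain an end-of-study specimen), will be used as the 6-month LDL-C value". No latest date is given.

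Section 6.1 covers the same participants, those who cannot attend for the end-of-study draw, and says: "The documented LDL-C value closest to the date 6 months after the date of randomization will be used for the end-of-study value". It then adds a fallback: "If no 6-month value is available, the study may use an LDL-C value obtained from the medical record" during the observation period, "including carry forward of the baseline value". It gives no window around the 6-month date and does not say whether closest means before, after or both. It does restrict record values used at baseline (at most 6 months old, no intervening change in lipid-lowering therapy), but it sets no matching limit at the end of the study.

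Section 6.2.1 determines target status "using the LDL-C values as described for the primary outcome in Section 6.1", so the target outcome falls under both rules as well. Section 3.1 places the Delayed arm's intervention at the end of the study, after 6 months. Section 5.3 places the final analysis after the last participant's data collection.

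**The concern.** Two binding rules define one measurement, and neither refers to the other. One participant can therefore have two legitimate 6-month LDL-C values, and two target classifications. With no precedence stated, the choice could be made after the data are seen.

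The 4.3.2 rule carries a further risk. It takes the latest value, and the only practical end point is the data extraction, so an early enrollee's value could date from long after month 6. The period it draws on begins about when disclosure to the Delayed arm falls due. A control value drawn after disclosure may already reflect the intervention, which would dilute both LDL-C contrasts.

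**Working it through.** **1. The two rules applied to the same records.** The records are invented. Days are counted from the 6-month date and no study draw was obtained.

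| Record values (day: mg/dL) | 4.3.2 | 6.1, closest in either direction | 6.1, if limited to on or after |
|---|---|---|---|
| -5: 150; +60: 110 | 110 | 150 | 110 |
| -20: 150; +10: 148; +200: 105 | 105 | 148 | 148 |
| -20: 150 only | none | 150 | none; optional fallback |
| +10: 148 only | 148 | 148 | 148 |

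Latest and closest select different measurements whenever two or more record values exist after month 6, however 6.1 is read. On the literal reading of closest, they also differ when the closest value lies before month 6. They agree when a single value satisfies both.

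**2. The plan's own figure.** Section 3.2 assumes -20% versus 0%, SD 30%, 80% power and alpha 0.05. By the normal approximation, n per arm = 2 × (1.960 + 0.842)² × 30² / 20² = 35.3, so 36 per arm and 72 in total, as stated. The sample size is not in dispute.

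**3. Dilution by control values drawn after disclosure.** Let D be the true difference in percentage points, f the share of Delayed values drawn after disclosure, and r the share of the effect realised by then.

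- Expected difference = D × (1 - f × r)
- Delayed-arm SD = √(SD² + f(1 - f)(rD)²)
- Standard error = √((SD² + Delayed SD²) / 122)
- Power from the noncentral t with 242 degrees of freedom, two-sided 0.05

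From Section 3.2 come D = 20 with SD 30, D = 15 with SD 40 (-20% versus -5%), and 122 per arm, kept whole because participants filled from the record stay in the analysis. D = 10 is 20 × 50%, from the allowance for no therapy escalation in half the Immediate arm, with SD kept at 30. The values of f and r are assumptions; f = 20% equals the plan's whole loss-to-follow-up allowance.

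Worked case, D = 10, f = 20%, r = 1: difference 10 × 0.8 = 8; Delayed SD √(900 + 0.16 × 100) = 30.27; standard error √((900 + 916)/122) = 3.86; ratio 8/3.86 = 2.07; power 54.2%.

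With r = 1 (difference; power):

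| D, SD | f = 0 | f = 5% | f = 10% | f = 20% |
|---|---|---|---|---|
| 20, 30 | 20; 99.9% | 19; 99.8% | 18; 99.6% | 16; 98.3% |
| 15, 40 | 15; 83.1% | 14.25; 79.0% | 13.5; 74.4% | 12; 64.1% |
| 10, 30 | 10; 73.7% | 9.5; 69.2% | 9; 64.4% | 8; 54.2% |

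With r = 0.5, f = 20% gives the same differences as f = 10% above, and power within about 0.2 points.

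**4. The LDL-C target outcome.** Take 60% meeting target in the Immediate arm against 40% + 20% × f in the Delayed arm, 122 per arm, pooled normal approximation. At alpha 0.05, the level used in Section 3.2, power is 88.3% at f = 0 and 84.8%, 80.7% and 70.8% at f = 5%, 10% and 20%. Section 5.4 applies Bonferroni to secondary outcomes. With the two listed in Section 6.2, alpha is 0.05/2 = 0.025, and power is 81.6% at f = 0 and 60.4% at f = 20%.

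**The case against.** The best defence is that 6.1 does not say closest on either side. Its fallback to values within the observation period would be largely redundant if closest already reached back before month 6, so the section may mean the closest value at or after month 6. That is a fair reading. It removes the conflict in the first invented record but not in the second. It also shows that 6.1 is unclear in itself, since without a window the fallback's trigger is undefined.

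A reader might infer that 4.3.2 contradicts its own 6-month observation period. That goes too far: a 6-month outcome is commonly measured at or just after month 6, and Section 4.3 speaks of approximately 6 months. The defect is the missing upper limit.

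A reader might also infer that the control arm will be contaminated, or that the trial loses its power. The SAP supports neither. A value counts only if the Delayed participant had no study draw, has a later record LDL-C, and had it drawn after disclosure. The SAP gives none of these shares, nor the actual disclosure date for someone without a specimen. The 20% case with full effect is an extreme, and even there power at the planned effect stays at 98.3%. The 10-point case is already below 80% without any late values. At f = 5% with half the effect realised, power moves only from 73.7% to 71.5%.

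Finally, baseline carry-forward and the open choice of imputation method in Section 5.5 are a separate question. They do not strengthen this contradiction.

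**Conclusion.** The point holds and must be fixed. For participants without an end-of-study draw, the primary outcome and the LDL-C target outcome have two selection rules that can give different answers, with no precedence. That stands on the text, at any frequency. It does not reach participants with a study draw or those whose only eligible record value satisfies both rules.

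The risk from values drawn after disclosure is real in direction but unknown in size. Under the stated assumptions the main harm at the planned effect is an estimate 1 to 4 points too small. Material power loss appears only at the smaller effects or on the target outcome.

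**What to change.** Use one rule in 4.3.2, 6.1 and 6.2.1:

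1. The end-of-study study draw.
2. Otherwise, the record value closest to the 6-month date within a prespecified window. Count the window from randomization, make it identical in both arms, and fix it before data are seen by arm. State whether it extends before month 6. Keep its upper limit short and choose it in light of when Delayed-arm results are actually returned.

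Delete the latest-value wording in 4.3.2. Define the absence of a 6-month value as no study draw and no record value inside the window. Report by arm how many values come from the record, and how many Delayed values follow disclosure. Add a sensitivity analysis with the same date cut-off in both arms; excluding late values from the Delayed arm alone would treat the arms differently.

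The cost is SAP wording and one further analysis. Disclosure falls due at about month 6, so a limit that must always precede it could leave almost no window after that date; this is why the limit has to be weighed and the remaining late values reported. Some record values will fall outside the window and become missing. The confidence interval widens by an amount that cannot be computed from the SAP.

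Secondary advice, outside the contradiction: for LDL-C still missing, prefer the within-arm multiple imputation that Section 5.5 already allows over single mean or median imputation, and keep baseline carry-forward as a sensitivity analysis.
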